***Long-term Quitting Study***

The analytic plan reflects that the treatments will be delivered in sequence (i.e., analyses will accommodate the transition of participants across the RR Preparation and RR Cessation treatments) as is recommended for SMART designs.

*Primary Aim.* To determine the effects of the RR Preparation treatment on abstinence at the Month 14 Preparation assessment time point amongst participants randomized to RR Preparation treatment (“active” and “control”). This analysis will be conducted using generalized linear models (GLM) with point-prevalence abstinence data as the outcome variable. Potential covariates will include: race, gender, tobacco dependence (e.g., before initial cessation treatment) and duration of abstinence in the initial cessation attempt. The main model will not control for RR Cessation factors; rather it will focus on the question of whether long-term differences in abstinence rates emerge from the RR Preparation treatment. These analyses will be done in several ways: 1) by comparing each active RR Preparation component with the Preparation Control condition, and 2) by conducting a GLM analysis comprising only the RR Reduction vs. Recycling Preparation participants. The former will address the issue of whether the active Preparation components, and any consequential access to RR Cessation treatment, affects the long-term smoking outcomes of participants. Results will be examined to determine the extent to which differences are related to the use of RR Cessation treatments. The second type of analysis will focus on the active RR Preparation components, when participants in each component have an equal chance of being assigned to any of the RR Cessation intervention components. RR Cessation factors will be used as covariates in supplementary analyses of the active components and the interactions of these factors with Preparation treatment condition will be examined. Marginal frequencies will be examined to determine the rate at which participants elect to be randomized to RR Cessation treatment.

*Secondary Aim 1.* We hypothesize that RR Reduction Counseling will lead to a greater likelihood of *meaningful* quit attempts and that these will occur at shorter latencies than RR Recycling Counseling. Even though Reduction participants will be encouraged to delay their quit attempts for 1 month of treatment, we predict they will be more successful than Recycling participants in sustaining early abstinence. All participants randomized to the non-control, active RR Preparation factors will be included in the following two analyses. First, we will use logistic regression to test for differences, due to Preparation factor, in the probability of a meaningful quit attempt during the 12 months after they enter RR Preparation treatment. Second, to examine latency to a new meaningful quit attempt, Cox Proportional Hazard models will be used to determine the hazard rate, with those not making a meaningful quit attempt treated as censored observations. Potential covariates will include: race, gender, tobacco dependence (e.g., before initial cessation treatment) and duration of abstinence in the initial cessation attempt (in subsequent analyses the type of RR Cessation treatment used will also be modeled as a covariate). These analyses will reflect Preparation effects comprehensively because they will reflect meaningful quit attempts that occur both with and without use of RR Cessation treatments. Then, only Preparation participants using RR Cessation interventions will be included in analyses of relations between RR Preparation and RR Cessation components as they influence meaningful quit attempts. This analysis will focus on whether type of RR Preparation treatment affects initial success (more than 1 day of abstinence at the start of the quit attempt) in an aided quit attempt, and whether this effect depends on type of RR Cessation treatment. We hypothesize that RR Reduction Counseling will produce stronger effects than

“Breaking Addiction to Tobacco for Health (BREATHE) Study”

PI: [name], MPH, MBA; UW-CTRI Center Grant: 1P01CA180945-01.

RR Recycling Counseling with regard to both the probability and latency of meaningful quit attempts, and we hypothesize that these effects will not interact with the RR Cessation factors.

*Secondary Aim 2.* To determine the main and interactive effects of the 2 RR Cessation factors on smoking abstinence following a quit attempt, and to determine whether these effects differ as a function of the RR Preparation factor. One analytic strategy will involve a 2x2 factorial analysis via a longitudinal generalized linear mixed-effects model (GLMM) with the 2 RR Cessation factors as independent variables, and RR Preparation factor as a covariate. Several outcomes will be analyzed. One outcome will be longitudinal abstinence across the 4 RR Cessation Follow-up time points ( Weeks 4, 10, 16, 26). A second will focus on survival analyses after the start of the participants’ course of RR Cessation treatment. Finally, a logistic regression analysis will be used to analyze abstinence reports at 26 Weeks post-RR Cessation treatment initiation. Only those who choose to make an aided quit attempt and are randomized to the RR Cessation factors will be included in these analyses, and all tests will be two-sided with  $p=.05$ . Additional potential covariates in the longitudinal models will include race, gender, and time since the initiation of the RR Preparation treatment (for the analysis examining long-term effects of RR Cessation treatment). We predict significant main effects for the enhanced level of each RR Cessation factor, but we predict no significant interaction effects between RR Preparation and RR Cessation factors; that is, we predict the RR Cessation factors will exert similar effects across the Preparation factor but we will test these relations. Because some participants randomized to Preparation treatment will not be included in this analysis (since they will not make aided quit attempts), this analysis will not capture the comprehensive effects of the Preparation factor. We are aware that the Preparation factor may cause different numbers or types of smokers to make aided quit attempts with the RR Cessation treatments. Such effects *might* moderate effects of the Preparation factor on the RR Cessation factors. However, this is not a limitation because this would be present in the real-world clinical effects of a Preparation treatment; e.g., such treatments could influence outcomes by better preparing smokers for cessation or by sending different types of smokers to an RR Cessation treatment.

Supplemental analyses will examine correspondence between CO levels at the 6 and 14 Month Preparation Phase follow-up and abstinence self-report at those and other time points (e.g., 10 months into the Preparation Phase). Adherence analyses will use Preparation Phase data and RR Cessation treatment contact data to analyze both patch and mini-lozenge use. Adherence will be evaluated with regards to both the RR Preparation phase (amongst Reduction participants) and in the RR Cessation Phase.

*Secondary Aim 3.* We will also examine “transition rates” across the phases of treatment: 1) To what extent do participants who relapse in response to Initial Cessation treatment, enter the RR Preparation treatment? 2) To what extent do participants who enter RR Preparation treatment remain in that treatment for 11 months? and 3) To what extent do participants who enter RR Preparation treatment decide to enter RR Cessation treatment? In other words, we will examine the extent that “chronic care” treatment “works” amongst relapsers, and the extent that this is related to type of “chronic care” provided. Do relapsers transition into chronic care and use its various resources? Such pragmatic analyses will be complemented by cost analyses regarding the various treatments analyzed.

*Secondary Aim 4.* We will also identify moderators and mediators of the effects of the RR Preparation and RR Cessation treatment factors. In keeping with the secondary aims of a

“Breaking Addiction to Tobacco for Health (BREATHE) Study”

PI: [name], MPH, MBA; UW-CTRI Center Grant: 1P01CA180945-01.

SMART trial, these moderator and mediator analyses will be useful for identifying candidate tailoring variables. For instance, a key mediator of RR Preparation Reduction treatment might be amount and persistence of smoking reduction. We will examine the relation between such reduction and success in RR Cessation treatment and also success as measured by outcome at the 7-, 10-, and 14-month Preparation phase assessment time points. Of course, smoking reduction will be analyzed as an outcome in its own right. All those assigned to RR Preparation conditions, including Control participants, can be included in such analyses, with outcomes assessed across the RR Preparation phase and at Month 14 follow-up.

For RR Cessation treatment moderation and mediation models, the outcome will be abstinence at 6 months after the RR Cessation target quit day. Mediation models (including multiple mediators) will use methods developed for use with dynamic mediator assessments (maximum likelihood estimation using hierarchical linear modeling: HLM 5.04, using RR Cessation treatment assessments and possibly data derived from Standard Assessment Staff calls) with binary outcomes (via a weighted least squares model in Mplus). Candidate mediators will include: demoralization, medication use, coping, smoking cue/trigger density, self-efficacy, craving, and smoking heaviness. Mediation effects will be tested using statistically powerful approaches (e.g., the joint significance test). Care will be taken to preserve mediator/outcome temporal priority, and the occurrence of smoking during the quit attempt will be statistically controlled when appropriate. Analysis of moderators will use both logistic regression (with model fitting techniques) and regression tree analyses to identify predictors of differential response to the RR Cessation components. Candidate moderators will include factors such as tobacco dependence and gender, and contextual factors such as household smoking.

Finally, while not a formal aim, we will also compare all possible types of “embedded adaptive treatments” on abstinence rates at the 7, 10, and 14 Month outcome time points. That is, we will compare the abstinence outcomes of groups of participants receiving the different unique combinations of RR intervention components. Logistic regression will be modified to weight for the fact that data for each participant are consistent with more than one adaptive intervention (an individual will receive multiple intervention components) and to accommodate the over/under-representation of outcomes based on the sequential randomization scheme. Embedded comparisons are typically underpowered in SMART designs but can be highly informative (viz. to check consistency with the factorial analyses).

**Clinic Randomized Control Trial**

**Primary Aim:** Using a multiple baseline design, determine the effects of a healthcare intervention package comprising a comprehensive set of EHR-based enhancements and a chronic care treatment for smoking, on rates of documentation of smoking status, referral to smoking treatment, and engagement in smoking treatment as compared to a usual care fax-to-quit referral to the Wisconsin Tobacco Quit Line.

**Power for Primary Outcomes in the three clinical studies and the clinic randomized control trial**

Power for each of the three studies was calculated based on the sample size and hypothesized effect sizes for each of the individual studies.

**Motivation Study**

“Breaking Addiction to Tobacco for Health (BREATHE) Study”

PI: [name], MPH, MBA; UW-CTRI Center Grant: 1P01CA180945-01.

We will enroll 512 participants. We will use an intent-to-treat principle for the primary abstinence analyses. Our factorial design takes advantage of all cells and participants, allowing us to analyze the entire sample for main effects. With two levels of each factor (e.g., BR Counseling or no BR), we will have 256 participants per group for analyses. We have based our power estimates on effect sizes found in our prior studies.

For cessation success, we conducted longitudinal power analyses. We computed power for the mixed effects longitudinal analysis using a SAS macro with the following parameters:  $N=256$  per group; smoking status assessed at 6 points (months 1, 2, 3, 4, 6, and 12); a drop-out rate of 10% at each successive time-point (higher than in Preliminary Study 1); a 10% versus 18% abstinence treatment effect modeled as a consistent effect over time; random effects variance=1; and within-subject correlation=0.6. We consider the targeted treatment effect (i.e., 8 percentage point difference: 10% vs. 18% among participants receiving an “on” intervention component) to constitute a clinically meaningful effect. Power for this scenario is 0.94 with a compound symmetry (CS) within-subject covariance structure; power is 0.99 with a first-order autocorrelation (AR(1)) within-subject covariance structure and correlation. Thus, the study is powered adequately to yield statistically significant treatment effects in the mixed effects analyses.

For quit attempts, we conducted single endpoint power analyses. We expect approximately 60% of participants to make a quit attempt on minimal treatment, as suggested by our Preliminary Study data. With a total  $N=512$ , there is adequate power (.81) to detect at least a 12 percentage point increase, a clinically meaningful increase, in quit attempts in the “on” treatment condition (72%) relative to the “off” condition (60%).

For smoking reduction, we conducted longitudinal power analyses. We calculated statistical power for a longitudinal mixed effects regression model for the smoking reduction outcome with two groups using the RMASS2 sample size program. We specified the following parameters for the program:  $\alpha=.05$ , two-tailed test, 6 time-points (months 1, 2, 3, 4, 6, and 12), attrition of 10% at each successive time-point (a high rate), within-subject correlation=0.6, a mean difference of 1.5 cigarettes (consistent across time), and a standard deviation of 7 (consistent across time). With attrition of 10% at each successive time-point, the retention rate decreased to 59% by the 12 month follow-up. These specifications yielded a composite effect size of .27 adjusted for attrition. With a sample size of 256 per group and adjustment for attrition, we have power of at least .85 to detect this effect size with AR(1) within-subject covariance structure and correlation.

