## PROTOCOL

### “Breaking Addiction to Tobacco for Health (BREATHE) Study”

PI: [name], MPH, MBA; UW-CTRI Center Grant: 1P01CA180945-01.

a Decisional Balance Questionnaire about smoking, assessments about whether they have been encouraged to quit, and assessments of recent quit attempts and plans for future quitting. Participants will complete 4 assessment calls at Weeks 12, 26, 39 and 52 (see Table 11). Only selected items from the above scales will be used for the subsequent assessment calls. Medication usage and side effects will be assessed at every study contact for participants using Nicotine Mini-Lozenge. NRT use and smoking will be assessed at each contact using the timeline follow back procedures.

**Intensive Longitudinal Data (ILD).** Participants will receive 11 brief, automated assessment calls over 52 weeks after Visit 1 (see Table 3 for schedule). The assessment schedule will continue even if a participant receives the cessation treatment to permit standardized assessments for all participants. The 3-4 min calls will occur shortly before bedtime, based on participants’ self-reported sleep times. This has resulted in acceptable call times in our previous research. The calls will assess: withdrawal symptoms (selected items from the Wisconsin Smoking Withdrawal Scale, including craving); positive and negative affect assessed via items from the PANAS; time to first cigarette in the morning; any smoking and use during the day of the call and during the preceding 7 day period; alcohol use, quit attempts and plans for quitting; pleasure from events; medication use; intrinsic motivation to quit or reduce smoking; and self-efficacy. Missed or deferred calls will be reinitiated in 15-minute intervals. Eligible participants must have access to a phone (either cell or land line). This assessment burden is much less than has been used successfully in many other studies, and research has shown that ILD/ecological momentary assessment produces modest assessment reactivity. Our prior experience shows that IVR systems yield high quality information with response rates exceeding 80%, even among primary care patients.

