**Motivation Study**

*Primary Aim 1: Determining the main and interactive effects of the intervention components on primary outcomes.* Our primary outcomes, assessed at both 6 months (end of treatment) and 12 months, are: 1) making a serious quit attempt (defined as  $\geq 48$  hours of nonsmoking as part of an intentional effort to quit); and 2) cessation success (defined as 7-day point-prevalence abstinence (PPA)—self-reported abstinence from smoking, even a single puff). With each of the components, we hypothesize that the "on" condition will produce higher quit attempts and cessation success than the "off" condition. Data for these aims come from phone assessments over the 12 months. We will model abstinence longitudinally via a mixed-effects logistic regression model including the main effects of treatment. Longitudinal models will include the effects of time, condition, and a random subject effect to account for the correlation of repeated assessments within subjects. We will also identify any interaction effects that emerge from the combinations of intervention components. For example, we will examine whether the combination of the BR and 5Rs has a larger or smaller effect than their additive

“Breaking Addiction to Tobacco for Health (BREATHE) Study”

PI: [name], MPH, MBA; UW-CTRI Center Grant: 1P01CA180945-01.

effects would predict. Although we will examine all possible interactions of the intervention components, we do not anticipate significant effects beyond 2-way interactions. *In sum, the proposed analyses will determine whether the tested intervention components, either via main or interaction effects, increase meaningful quit attempts and long-term abstinence rates.* In addition, we will use logistic regression analyses with effects-coding to examine the effect of each intervention component on the occurrence of the binary outcomes of quit attempt occurrence and PPA at different follow-up points. Models will include only main effects and two-way interactions; no higher-order interactions are expected. Following the intent-to-treat principle, all 512 participants randomized to treatment will be included; missingness will be investigated in other analysis

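### Motivation Study: abstinence power is stated on a six-point grid that matches neither the 6- and 12-month outcomes nor the assessment calls, and single-time abstinence power (about 0.74) is not given

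*Combined protocol and SAP*

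**What the plan says.** All references are to the combined protocol and SAP.

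- **Analytic Plans, Motivation Study, Primary Aim 1.** The primary outcomes are a serious quit attempt and 7-day point-prevalence abstinence, "assessed at both 6 months (end of treatment) and 12 months". On the data source it says "Data for these aims come from phone assessments over the 12 months". The first-named abstinence analysis is a longitudinal mixed-effects logistic model with "a random subject effect to account for the correlation of repeated assessments within subjects". In addition, logistic regressions are planned for the "binary outcomes of quit attempt occurrence and PPA at different follow-up points". On the analysis set: "all 512 participants randomized to treatment will be included; missingness will be investigated in other analysis".
- **Power, Motivation Study.** Abstinence power is computed for the longitudinal model with "smoking status assessed at 6 points (months 1, 2, 3, 4, 6, and 12", 256 per group, 10% vs 18%, 10% drop-out per successive time point and within-subject correlation 0.6. The results are 0.94 (compound symmetry, CS) and 0.99 (AR(1)). Single-endpoint power is given for quit attempts only: .81 for 60% vs 72%.
- **Data Collection, Motivation Study.** "Participants will complete 4 assessment calls at Weeks 12, 26, 39 and 52". It also says "NRT use and smoking will be assessed at each contact using the timeline follow back procedures", and the automated (IVR) calls ask about smoking over the preceding 7 days.
- **Treatment length.** Table 3 schedules counseling to Week 47. The Intervention Components section describes 12 months of mini-lozenge use and 52-week periods for all three counseling components. The Cessation Phase paragraphs, under Study Procedures and Intervention Components, speak of 9 months.

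**The concern.** A power statement should describe the analysis that will be run. Here three sets of time points are in play: six in the power calculation, two in the outcome definition and four in the assessment-call schedule. The plan does not say which visits, or which source (assessment calls, follow-back or automated calls), enter the longitudinal model.

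Two power figures are quoted, and the more favourable one rests on a correlation structure that the analysis section does not name. The single-time abstinence tests have no stated power. The Cessation Study section, by contrast, reports both a longitudinal figure (0.91) and a 6-month single-time figure (.80).

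The Motivation Study is meant to screen components. A reader who takes 0.94 or 0.99 as the chance of detecting an 8-point effect at 6 or at 12 months would be misled.

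Separately, calling 6 months the end of treatment leaves it unclear whether the 12-month outcome falls during or after treatment.

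**Working it through.** **Inputs.** 256 per level of a factor; 10% vs 18%, constant over time; 10% loss per time point; correlation 0.6 (Power, Motivation Study, abstinence). Alpha 0.05 two-sided is stated for smoking reduction but not for abstinence, so it is an assumption here. The smoking-reduction paragraph gives 59% retention at month 12. This equals 0.9^5, so the first point is taken as fully observed.

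**Step 1: the plan's own figures.** The plan does not state the scale of the 0.6. Read as a latent-normal correlation, it gives an observed binary correlation ρ of 0.322 at 10% and 0.363 at 18%. Under CS a participant seen at k visits contributes k/[1+(k−1)ρ] effective observations. Let m be the average of this over the drop-out pattern. The variance of the risk difference is then [0.09/m₁ + 0.1476/m₂]/256.

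For six points, the proportions last seen at points 1 to 6 are 0.100, 0.090, 0.081, 0.073, 0.066 and 0.590. These give m₁ ≈ 2.03 and m₂ ≈ 1.90. The SE is √[(0.0443+0.0775)/256] ≈ 0.0218, so z = 0.08/0.0218 ≈ 3.67 and power = Φ(3.67−1.96) ≈ 0.956. The logit scale gives 0.952. If loss starts at the first point, the values are 0.936 and 0.931. AR(1) gives 0.976 to 0.988. The plan's 0.94 and 0.99 are therefore roughly reproduced.

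**Step 2: which structure applies.** A random subject effect alone makes all pairs of visits equally correlated. That is CS, so 0.94 is the matching figure.

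**Step 3: do the grids match?**

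| Power grid | Assessment call | Other contact (Table 3) |
|---|---|---|
| Month 1 | none | IVR Week 4 |
| Month 2 | none | IVR Week 9 |
| Month 3 | Week 12 | |
| Month 4 | none | IVR Weeks 15, 18 |
| Month 6 | Week 26 | |
| not in grid | Week 39 | |
| Month 12 | Week 52 | |

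**Step 4: the four assessment calls, CS, latent 0.6.**

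- With 10% loss per call from a full first call, m₁ ≈ 1.87 and m₂ ≈ 1.77. The SE is about 0.0227, z ≈ 3.53 and power ≈ 0.941. Across scales and with loss starting at the first call, the range is 0.91 to 0.94.
- With the plan's loss placed on the calendar (0.81, 0.656, 0.622 interpolated, 0.590), m₁ ≈ 1.46 and m₂ ≈ 1.39. The SE is about 0.0256, z ≈ 3.12 and power ≈ 0.878. The logit scale gives 0.870.

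**Step 5: single-time tests.** First a check on quit attempts: 60% vs 72%, 256 per group, two-sided 0.05 gives 0.819 against the stated .81.

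For abstinence with all 512 counted, the pooled rate is 0.14. Power = Φ{[0.08×√256 − 1.96×√(2×0.14×0.86)]/√(0.09+0.1476)} = Φ[(1.280−0.962)/0.4874] = Φ(0.653) ≈ 0.743. The unpooled form gives 0.747 and the logit Wald test 0.731. Power of 0.80 would need about 295 per group (292 to 303 by method), or a rate of about 18.6% to 18.8% against 10%.

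If only observed participants are analysed under the plan's drop-out, n is 256×0.656 ≈ 168 at month 6 and 256×0.590 ≈ 151 at month 12. Power is then 0.56 and 0.52.

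**The case against.** The strongest reply is that the power section does address the right class of analysis. The longitudinal model is the first-named abstinence analysis, and the adequacy statement is limited to the mixed-effects analyses. Months 6 and 12 are two of the six points, and the effect is modelled as constant over time. The automated calls at Weeks 4, 9, 15 and 18 carry a 7-day smoking item, so months 1, 2 and 4 can be approximated. Mediation Aim 2 refers to those calls as phone assessments, so the stated data source may include them. All of this stands. It reduces the mismatch to visits and sources that the plan does not name, and it means that 0.74 does not replace 0.94.

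A reader might infer that the longitudinal analysis is underpowered. A model using months 6 and 12 only, with 66% and 59% observed, would have 0.71 to 0.72. That case is hypothetical: no part of the plan proposes a two-visit model on observed data only, the plan includes all 512, and it describes 10% loss per point as a high rate. With no loss the two visits give 0.88 to 0.89.

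A reader might also take 0.6 as the correlation between the binary responses themselves, which lowers every longitudinal figure. That reading does not reproduce 0.94 and 0.99, so it is no basis for a criticism.

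Finally, the single-time tests are additional analyses, and the plan does not say that components will be selected on them alone. This is why labelling them supportive is an acceptable remedy.

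**Conclusion.** The point holds in a limited form. The stated abstinence power belongs to a grid that matches neither the primary outcome times nor the assessment calls, and 0.99 belongs to a correlation structure that the planned model does not name. No arithmetic error in 0.94 or 0.99 is shown. On the four calls the longitudinal analysis keeps about 0.87 to 0.94, so the plan's claim of adequate power survives for that analysis. This rests on a latent 0.6, CS, two-sided 0.05 and the retention patterns shown.

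The omission that matters is the single-time power of about 0.74 (0.73 to 0.75 by method), with all 512 counted. An 8-point effect would be missed at a given time about one time in four, and more often if only observed participants are analysed.

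The end-of-treatment label is a separate and real contradiction: no treatment period given elsewhere ends at 6 months. A reader might infer that the plan claims durability after treatment at 12 months. It makes no such claim; it only leaves the timing open.

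**What to change.** 1. In Primary Aim 1, name the visits and the data source (assessment calls, follow-back or automated calls) that enter the longitudinal abstinence model.
2. Restate the power on those visits under CS, with the alpha, sidedness and retention used. Drop 0.99, or mark it as not matching the planned model. Saying which scale the 0.6 refers to would help the reader but is only added detail.
3. Report about 0.74 for the single-time 6- and 12-month abstinence tests, with the condition that all 512 are counted, or label those tests supportive and not powered.
4. Reconcile the 6-month end-of-treatment label with Table 3, the Cessation Phase paragraphs and the Intervention Components section, and state whether the 12-month outcome falls during or after treatment.

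The cost is one rerun calculation and some changes of wording. The only downside is a less favourable stated power. No participants, visits or calls are added.

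### The .81 power for the Motivation Study quit-attempt outcome holds only if every participant's outcome is known; the section's other calculations allow for loss

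*Combined protocol and SAP*

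**What the plan says.** The Motivation Study part of Analytic Plans names two primary outcomes at 6 and 12 months: a serious quit attempt and 7-day point-prevalence abstinence. It adds that "all 512 participants randomized to treatment will be included" and defers missingness to other analyses. It gives no rule for coding a quit-attempt outcome that was never obtained.

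The Motivation Study part of the power section starts from "We will enroll 512 participants" and, for each two-level factor, "we will have 256 participants per group for analyses". It then makes three calculations:

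- **Cessation success** (longitudinal) includes "a drop-out rate of 10% at each successive time-point (higher than in Preliminary Study 1").
- **Quit attempts:** "For quit attempts, we conducted single endpoint power analyses". The inputs are 60% versus 72% and a total of 512. The result is that "there is adequate power (.81) to detect at least a 12 percentage point increase". No drop-out rate, alpha or sidedness is given.
- **Smoking reduction** (longitudinal) uses a two-tailed .05 test and the same 10% per time-point, described there as high, and reports that "the retention rate decreased to 59% by the 12 month follow-up".

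**The concern.** Of the three calculations, only the one for quit attempts treats the enrolled number as the analysed number. Enrolment of 512 contains no allowance for loss, so any missing outcome must reduce the information behind the .81.

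The study screens four components for a later treatment package, and the protocol calls a 12-point increase in quit attempts clinically meaningful. If true power is below the stated figure, a component with that effect is more likely to be dropped, and a null result will be read with more confidence than it deserves. The abstinence outcome is not affected, because its stated power (.94 or .99) already includes drop-out.

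**Working it through.** **Inputs.** Quit-attempt rates of 60% and 72%, and 256 per level, come from the Motivation Study power section. Two-sided .05 is an assumption taken from the smoking-reduction calculation, because none is stated for quit attempts.

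**Formula.** For n per level, rates p1 and p2, and p̄ their mean:

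se0 = √[2p̄(1−p̄)/n]; se1 = √[p1(1−p1)/n + p2(1−p2)/n]; power = Φ[(|p2−p1| − 1.96·se0)/se1].

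**Reproducing the stated figure.** With n = 256:

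- se0 = √(2 × .66 × .34/256) = .0419
- se1 = √[(.24 + .2016)/256] = .0415
- power = Φ[(.12 − 1.96 × .0419)/.0415] = Φ(.913) = .82

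The unpooled, arcsine and exact chi-square versions also give .82, and a continuity correction gives .79. The printed .81 is therefore the zero-loss result.

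**Retention scenarios.**

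- *The section's planning case.* Six time-points with 10% lost at each after the first give 0.9^5 = 59% at month 12, which is a 41% loss.
- *The calls actually scheduled.* Motivation assessment calls are at Weeks 12, 26, 39 and 52. With the first complete and 10% lost at each later call, retention is 0.9 = 90% at Week 26 and 0.9³ = 73% at Week 52, which is a 27% loss.
- *Milder values.* 5% and 20% total loss are illustrative.

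**Power when loss is allowed for.** In the third column, n is 256 × retention and the rates stay at 60% and 72%. In the fourth, n stays at 256 and both rates are multiplied by retention.

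| Loss | Retained per level | Power, retained only | Power, all 256, lost = no attempt |
|---|---|---|---|
| 0% | 256 | .82 | .82 |
| 5% | 243 | .80 | .76 (57.0% vs 68.4%) |
| 10% | 230 | .78 | .70 (54.0% vs 64.8%) |
| 20% | 205 | .73 | .59 (48.0% vs 57.6%) |
| 27% | 187 | .69 | .51 (43.7% vs 52.5%) |
| 41% | 151 | .60 | see the objection |

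**Crediting attempts reported before drop-out.** A quit attempt is cumulative, so a participant lost late may already have reported one. This check keeps all 256 per level, uses the section's six-point attrition, and counts attempts up to each participant's last contact. Power is .47 if attempts are uniform over 12 months, .58 if all fall uniformly in the first 6 months, and .59 under a constant hazard.

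**Scale of the missing allowance.** By the formula above, .81 needs 250 per level with outcomes known. At 41% loss that means enrolling 250/(1 − .41) = 424 per level, or 848 in total, against the planned 512.

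**The case against.** The strongest reply is that the attrition rate is borrowed. It is stated for cessation and smoking reduction, not for quit attempts, and the protocol itself calls it high and above what its preliminary study saw. It also rests on six time-points that do not match the four scheduled calls. All of this stands. A reader might infer that the design will deliver only .60, or about .64 to .65 at month 6 from 0.9⁴ = 66% retention. The documents do not support either as a forecast: the first is a deliberately conservative case, and the second is a retention figure the protocol never states.

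A reader might also keep all 512, count everyone lost by month 12 as no attempt, and get .38 (35.4% vs 42.5%). That is not a realistic scenario. Quit attempts are asked about at every assessment call and on the 11 automated calls, so many attempts would be on record before a participant was lost.

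A third reply is that the 60% from preliminary data might already count non-responders as no attempt, which would make the use of all 512 coherent. The documents do not settle this. Both 60% and 72% exceed 59%, so at the section's own retention they cannot be rates that count everyone missing at the 12-month call as no attempt. With milder loss, or with earlier attempts credited, they could be.

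Finally, including all 512 under intent-to-treat does not by itself preserve power. It keeps the denominator, but without a rule for missing outcomes it says nothing about the difference that remains.

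**Conclusion.** The concern holds in a limited form. It would be a mistake to read .81 as a calculation error, because it reproduces. What is wrong is that the figure is offered as adequate power without saying that it needs every quit-attempt outcome to be known, while the calculations on either side of it assume loss.

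The figure has almost no margin: about 5% loss already brings it to .80. Over the plausible range it is .78 to .69 among those retained (10% to 27% loss), and .60 in the section's conservative case. At .60, a true 12-point effect would be missed about 40% of the time, against 19% as stated.

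These results assume a two-sided .05 test, rates of 60% and 72% among those whose outcome is known, and equal loss in the two levels of a factor. Only this primary outcome is affected.

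**What to change.** In the Motivation Study power section, restate the quit-attempt power with the section's own attrition shown as the conservative case (about .60 at 12 months), next to a milder range such as .78 at 10% loss, .73 at 20% and .69 at 27%. In the same place, state alpha and sidedness, and say how a missing quit-attempt outcome is counted in the calculation, including whether attempts reported before drop-out are credited. The alternative is one added sentence saying that .81 requires complete outcome data on all 512.

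Either change costs a sentence or two and a less favourable number. Design, sample size and data collection stay as they are.
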